C. Long Term Objectives: 1) To decrease the long term risks associated with obesity such as coronary artery disease and diabetes in the SMI population. 2) To promote recovery, improve mental health, quality of life, and treatment adherence, and to decrease utilization of hospital resources by improving the overall medical and psychiatric condition of these patients. 3) To create a user-friendly intervention program that is easy to disseminate and implement and can be provided by any motivated health care provider in any mental health setting. 4) Finally, we wish to network with other mental health providers and create an educational website that will allow us to disseminate the program further outside of our 4 sites. Specifically, we think this will be helpful to ultimately disseminate this manualized long term weight loss program to other mental health programs such as PRRCs that are being established by the Uniformed Services Package throughout the country (3).

D. Hypotheses

1. Primary Hypotheses:

a) Veterans with SMI at four different sites with antipsychotic associated obesity who participate in the 12-month multi-modal, MOVE-like, intervention that includes classes of the Lifestyle Balance Program, and individualized lifestyle balance coaching, will gain more knowledge (i.e., greater change scores on before/after survey test instrument) about general health issues (e.g., nutrition, importance of exercise, etc.) than a control group receiving "usual psychiatric care."

b) Subjects randomized to active treatment in the 12-month, Lifestyle Balance Program will make more objective lifestyle changes (as measured by exit interviews, food and exercise diaries, fidelity assessments) than those in the usual psychiatric care group.

c) Subjects who participate in the 12-month multi-modal Lifestyle Balance Program will achieve better cardiovascular (e.g., sustained weight loss, better glucose tolerance, improved lipid profiles) and mental health (e.g., improvements in recovery from mental illness, improvement in biopsychosocial/spiritual wellness [measured by the WHO-QOL BREF and the BPSS], general measures of psychopathology, subjective quality of life, etc) outcomes than the control group.

2. Secondary Hypotheses:

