maintenance. Precontemplation is the stage at which there is no intention to change behavior in the foreseeable future. Many individuals in this stage are unaware or underaware of their problems. Contemplation is the stage in which people are aware that a problem exists and are seriously thinking about overcoming it but have not yet made a commitment to take action. Preparation is a stage that combines intention and behavioral criteria. Individuals in this stage are intending to take action in the next month and have unsuccessfully taken action in the past year. Action is the stage in which individuals modify their behavior, experiences, or environment in order to overcome their problems. Action involves the most overt behavioral changes and requires considerable commitment of time and energy. Maintenance is the stage in which people work to prevent relapse and consolidate the gains attained during action. For addictive behaviors this stage extends from six months to an indeterminate period past the initial action. Most of the patients who will join this study will do so presumably, because they are at the Action stage in this hierarchy. Patients' motivational state will be assessed at baseline, 8 weeks, 6 months, 12 months, and end of study utilizing the URICA, a validated and reliable measure of motivation (70).

g) Biopsychosocial/spiritual Wellness Self Report Scale. To measure the sense of wellness the patient has in biological, psychological, social and spiritual realms, this scale is a 4 item scale with a maximum of 10 points per item reflecting level of wellness that the patient feels.

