a) SMI patients with antipsychotic associated obesity who participate in a behavioral intervention that includes classes on Lifestyle Balance will gain more knowledge (i.e., greater change scores on before/after survey test instrument) about general health issues (e.g., nutrition, importance of exercise.) than a control group receiving “usual psychiatric care”.

b) SMI patients with antipsychotic associated obesity who participate in a behavioral intervention program will achieve better cardiovascular (e.g., sustained weight loss, better glucose tolerance, improved lipid profiles, and improvement in other biological measures, e.g. insulin and c-reactive protein) and mental health (e.g., improvements in general measures of psychopathology, subjective quality of life, etc) outcomes than the control group. A larger proportion of patients who take the Lifestyle Balance classes will actually make lifestyle

changes (objectively measured by food and exercise diaries) than patients in the usual care group given ordinary counseling.

c) A larger proportion of patients who take the Lifestyle Balance classes will actually make lifestyle changes (objectively measured by food and exercise diaries and exit interviews) than patients in the usual care group given ordinary counseling. Analysis plan: For all hypotheses concerning the effects of the treatment program use analysis of repeated measures using the assessments at baseline, 8 weeks, 6 months, and 12 months. These analyses will provide information about maintenance of treatment effects. We will use a mixed general linear model with timepoints nested within patients. For hypothesis (c) we will adapt the mixed general linear model to dichotomous data by using a logistic link function to model the likelihood of life style changes. We will include all patients with at least one post-baseline data point in the analysis to maximize power. We will also consider the appropriateness of linear growth curve mixed effects models, i.e., fitting an intercept and linear slope for each treatment group as fixed effects, and separate intercepts and linear slopes for each patient as random effects. Analyses of linear trends over time with a single df effect are often more powerful tests of differences in trends than multiple df profile contrasts across the separate time points.

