General linear mixed effects models permit missing data but assume that data are missing at random. We will explore this assumption by comparing attrition rates in the study groups, and by comparing patients with and without post-treatment data on baseline scores and other baseline characteristics. If missing at randomness does not seem like a valid approach we will use multiple imputation based on different models of missingness to determine the degree of potential bias due to the way we approach the problem of missing data. Based on our experience with similar data we don't expect the data to violate missingness at random, but if it does we will use the results of the multiple imputation based on the EM algorithm to derive confidence intervals for our parameter estimates.

For Primary Hypothesis C, intraclass correlations will be run to assess the concurrent validity of the BPSS (compared to the WHO-QOL) to examine the relationship between study participation and biopsychosocialspiritual wellness.

Secondary Hypotheses:

a) Negative and Cognitive Symptoms will affect weight loss. Specifically we hypothesize: i.) High levels of negative symptoms as rated by the BPRS negative symptom cluster will correlate negatively with weight loss; ii.) Motivation to change level will impact weight loss directly; iii.) High levels of cognitive impairment as measured by the BPRS cognitive cluster will correlate with low weight loss, and; iv.) Insight into illness (as measured by the SAIQ) will correlate directly with weight loss. v.) High motivation as measured by the URICA will correlate with successful weight loss

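### The planned intraclass correlation can understate the concurrent validity of the BPSS against the WHO-QOL, and it cannot examine the effect of participation on wellness

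*Combined protocol and SAP*

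**What the plan says.** Section V.N.4 (Statistical Plans), after the missing-data paragraph, states that for Primary Hypothesis C "intraclass correlations will be run to assess the concurrent validity of the BPSS (compared to the WHO-QOL". The same sentence gives the purpose: "to examine the relationship between study participation and biopsychosocialspiritual wellness". It does not state the form of ICC (consistency or absolute agreement), whether scores are standardised, the visit, or whether the arms are pooled.

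Other places bear on how to read that sentence:

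- **Section I.D.1(c)** lists biopsychosocial/spiritual wellness, "measured by the WHO-QOL BREF and the BPSS", among the outcomes expected to be better than in the control group.
- **Section V.G.4(g)** describes the BPSS: "this scale is a 4 item scale with a maximum of 10 points per item reflecting level of wellness that the patient feels". No section gives the number of items, range, mean or SD of the WHO-QOL.
- **Section V.N.4, analysis plan for the primary hypotheses**, has a general rule: "For all hypotheses concerning the effects of the treatment program use analysis of repeated measures", with assessments at baseline, 8 weeks, 6 months and 12 months. Section V.N.3 makes a two-group mixed model the primary design for continuous scales.
- **Section V.N.4, hypothesis (c)** concerns lifestyle change, "objectively measured by food and exercise diaries and exit interviews". The reference to Primary Hypothesis C therefore fits the lettering of section I.D, not that of the section in which it stands.
- **The Schedule of Events** has a BPSS row marked at baseline, 8 weeks, 6 months and 12 months. It has no row named WHO-QOL. Section V.G.4(c) describes a different quality-of-life interview, given at baseline and one year.

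**The concern.** Concurrent validity asks whether patients who score high on one instrument also score high on an established one. An ICC on raw scores asks something narrower: whether the two numbers agree as if they were repeat measurements in the same units. The BPSS and the WHO-QOL are separate instruments, and nothing in the plan puts them on a common metric. If their spreads differ, the ICC falls even when the ranking of patients is identical, and a reader could take a low value as evidence against the BPSS.

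The stated purpose is a second problem. An ICC between two questionnaires completed by the same patients contains no comparison of arms. It is also the only sentence in the statistical section that names the BPSS, so an analyst who follows the specific instruction might take it as the analysis of participation and wellness.

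**Working it through.** The plan gives no target, precision or sample size for this ICC, so there is no stated figure to reproduce.

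**Inputs.** From the documents: the BPSS has 4 items of at most 10 points each (4 × 10 = 40 if they are summed, which the text does not state). Assumed, because the documents are silent: correlation r between the instruments; SD ratio k (WHO-QOL SD divided by BPSS SD) from 1 to 4; mean gap D from 0 to 4 BPSS SDs.

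**Formulas** (two measures, BPSS SD set to 1):

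- consistency ICC = 2rk / (1 + k²)
- absolute-agreement ICC = 2rk / (1 + k² + D²)

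**Consistency form:**

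| k | r = 1.0 | r = 0.7 |
|---|---|---|
| 1 | 2/2 = 1.00 | 1.4/2 = 0.70 |
| 2 | 4/5 = 0.80 | 2.8/5 = 0.56 |
| 2.5 | 5/7.25 = 0.69 | 3.5/7.25 = 0.48 |
| 4 | 8/17 = 0.47 | 5.6/17 = 0.33 |

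A mean difference has no effect on this form; equal SDs are enough for it to equal r.

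**Absolute-agreement form at k = 2.5:** with r = 1, 5/(7.25 + 4) = 0.44 at D = 2 and 5/(7.25 + 16) = 0.22 at D = 4. With r = 0.7 and D = 4, 3.5/23.25 = 0.15.

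**The ICC still carries information on association.** At k = 2.5 the consistency ICC is 0.35, 0.48, 0.62 and 0.69 for r = 0.5, 0.7, 0.9 and 1.0. On standardised scores it equals the Pearson correlation: in simulation (4,000 runs, n = 66, true r = 0.7, no group effect) both averaged 0.697.

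**Participation.** The same simulation, with k = 2.5 and D = 4, added a group effect to both instruments:

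| True group effect (SD) | Consistency ICC | Absolute-agreement ICC | Simple between-arm difference on BPSS (SD) |
|---|---|---|---|
| −0.5 | 0.492 | 0.182 | −0.501 |
| 0 | 0.481 | 0.150 | −0.005 |
| +0.5 | 0.495 | 0.142 | +0.505 |

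The consistency ICC barely moves and gives nearly the same value for harm and benefit. The absolute-agreement ICC does move, but only because a group effect changes the mean gap between two instruments with different SDs: the average gap is 4 + 0.5 × (2.5 − 1) × (−0.5) = 3.625 under harm and 4.375 under benefit. Neither compares the arms. The between-arm difference recovers the effect.

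**The case against.** The strongest reply is that the between-arm question already has an analysis. Section I.D.1(c) makes BPSS and WHO-QOL wellness an outcome compared with control. Section V.N.4 applies a repeated-measures mixed model to every treatment-effect hypothesis, at the same four time points as the BPSS row in the Schedule of Events, and V.N.3 makes that model a two-group one. On this reading the ICC sentence is a supporting validation step for a short self-report scale. This stands. A reader might infer that the wellness component of a primary hypothesis has no test of treatment; the documents do not support that. What remains is that the model text does not name the BPSS, and that the one sentence which does name it gives the ICC a purpose it cannot serve.

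A second reply is that the form of ICC and any scaling are unspecified, so the statistic is not necessarily wrong: on standardised scores it is simply the Pearson correlation. This also stands in part. A reader might conclude that the ICC measures only a mismatch of units and nothing about validity. That goes too far, since at a fixed metric it rises with r. But the plan does not say that scores are standardised, and if they were, the ICC would add nothing to an ordinary correlation.

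A third reply is that the WHO-QOL metric is not given, so a difference in spread is not demonstrated. That is correct, and it limits what can be said about size.

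**Conclusion.** The point holds as a correction to a stated method. On unstandardised scores the planned ICC can understate the concurrent validity of the BPSS, and in any form it cannot examine participation. The second conclusion needs no assumed figure, because the statistic has no treatment term.

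The size of the first depends on the unknown WHO-QOL SD and, for absolute agreement, its mean. Over SD ratios of 1 to 4, a perfect correlation would appear as a consistency ICC between 1.00 and 0.47. At a ratio of 1 nothing is lost.

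A reader might also infer that the BPSS would be reported as invalid. The plan sets no ICC threshold or decision rule, so the most that can be said is that a low value could be misread. The consequence is confined to the validity result and to clarity about which analysis answers the wellness question; no treatment-effect test depends on the ICC.

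**What to change.** 1. In section V.N.4, replace the ICC with a Pearson or Spearman correlation between BPSS and WHO-QOL, with a 95% CI, at a named visit. The plan already uses Pearson correlations for secondary hypothesis (a). Baseline would avoid any treatment effect entering a pooled correlation; in the simulation at n = 66, a +0.5 SD effect on both instruments moved the pooled Pearson value only from 0.697 to 0.717.
2. Delete the statement that this analysis examines participation and wellness.
3. Name the BPSS (baseline, 8 weeks, 6 and 12 months) as an outcome of the mixed model in section V.N.4, and align the hypothesis lettering between I.D and V.N.4 so that it is clear which model applies to wellness.
4. Reconcile sections I.D.1(c) and V.N.4 with the Schedule of Events, which has no row named WHO-QOL, and state the visits at which the comparator is available. Without this, the visit in step 1 cannot be fixed.

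The cost is minor SAP editing with no added BPSS visits, provided the WHO-QOL is in fact collected. If it is not, the validity analysis cannot be run as described under any choice of index.

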Prior to statistical analyses, the data will be inspected to determine the advisability of scale transformation to normalize distributions or reduce variance heterogeneity (e.g., logarithmic or power transformations) and to identify missing data, outliers, or other unusual features that might bias results. Where multiple measures may overlap or be redundant, preliminary analyses will explore whether it is possible to reduce these using techniques from scale development such as factor analyses. Preliminary analyses are also performed to compare treatment groups on descriptive and clinical characteristics at baseline to ensure randomization has succeeded. If there are significant differences between the treatment groups at baseline we will create propensity scores and include them in all further analyses as covariates to compensate for potential bias. We will also test if there are significant site effects, and if necessary we will include a site variable in the mixed linear model analysis, and model time as nested in subjects and subjects nested in sites.

To address concerns about excessive Type I error rates, the principal analyses are designed to answer clearly stated major research hypotheses, and are based on well-specified dependent variables. The samples are large enough to expect that confidence limits may be reasonably narrow, and findings may be robust enough to permit conservative adjustments of p-values for multiple testing. Bonferroni and other adjustments are necessarily somewhat arbitrary as Saville notes in his argument against their use (71). Additional analyses that are exploratory will be clearly identified as such. All tests will be two-tailed at $\alpha=0.05$.

2. Attrition: Dropout from treatment does not necessarily mean participants will refuse follow-up assessments, and we will attempt to obtain full follow-up data on all enrolled participants regardless of degree of participation and include all enrolled participants in analyses when any outcome data are available (intent to treat). Attrition can compromise randomization, so preliminary analyses will compare baseline characteristics

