of subjects available for analysis at each data point with those who are missing to evaluate sampling biases. Attrition naturally lends itself to analysis using survival regression models. Rates of attrition in the treatment groups will be depicted using Kaplan-Meier curves and simple comparisons performed using the log-rank test. More detailed examination of covariates that may predict dropout will be done using proportional hazard survival regression, which permits entry of both fixed (e.g., baseline status or descriptive-demographic characteristics) and time-dependent covariates that change over time (e.g., change in clinical status on prognostic variables). Dropout information is known for all subjects, so multiple logistic regressions can also be employed to evaluate multiple predictive factors without attention to timing of dropout. If trajectories of change on clinical outcome variables or interim (six month) data predict dropout, that would be taken into account in interpretation of the outcome analyses (e.g., sampling bias). We will compare subjects included in the analyses at any point with those who have dropped out on variables such as overall change from baseline, trajectory (slope or speed of change), and status at the last data point. There is no perfect statistical solution to missing data, but if dropout is deemed to be a possible source of bias in the analysis, we will consider additional analyses that specifically address sampling bias (e.g., two-stage modeling, propensity score stratification (72, 73)) weighted analyses or sensitivity analyses such as multiple imputation that examine the robustness of findings to assumptions about the outcomes of lost cases. As noted below, the proposed longitudinal (repeated measures) analyses are likelihood-based general (or generalized) linear mixed models, which permit missing data (see (74) for a recent, explicit comparison of five alternative data analysis approaches to the missing data problem which strongly cautions against analyses based only on complete cases and comments favorably on the use of linear mixed model methods).

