Analysis plan: We do not expect to see meaningful weight loss in the usual care group, and thus do not expect meaningful correlations based on these hypotheses. Accordingly, the primary tests of each of these hypotheses will be done by computing Pearson correlations between the specified variables within the treatment group. Supplementary analyses will be done within the context of the mixed effects designs described above, including these variables as possible treatment effect moderators. Separate analyses for hypotheses (i.) through (iv.) above will be done to examine possible interactions of each of these variables considered separately with treatment group. These analyses will test whether treatment may be more or less effective as a function of these variables (negative symptoms, motivation to change, cognitive cluster, insight). If so, we will stratify the groups according to these variables to simplify presentation of the results, e.g., treatment outcomes presented separately in groups with more versus less cognitive impairment).

b) SMI patients involved in the Lifestyle Balance Program will have better adherence to psychiatric treatment than the Usual Care group as measured by percent of psychotropic medication refills and percent of appointments attended.

Analysis plan: We will compute these dependent measures (percent of psychotropic medication refills and percent of appointments attended) to create summary scores within each of the three study follow-up epochs (baseline- 8 weeks, 8 weeks- 6 months, 6-12 months). These will be analyzed using general linear mixed effects models with repeated measures, including baseline stratification medication as a covariate. We will test group, time and interaction effects, and perform between-group contrasts for each time period.

To determine what patient characteristics, e.g. Medication group, diagnostic or symptom status is most conducive to positive outcome we will use classification analysis using the recursive partitioning algorithm to determine which patient characteristics at baseline are the best predictors for positive outcomes. Recursive partitioning is a computationally intense data mining technique that allows for the analysis of multiple predictors simultaneously while protecting against type I error inflation due to multiple testing and it provides non-parametric confidence intervals by using cross-validation (75).

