It provides valid statistics even in cases where there are more potential predictors than observations, and allows us to include all demographic, psychosocial, psychiatric and medical data known at baseline as potential predictors. The results of this analysis will suggest which patients are most likely to profit from further interventions, and it will also characterize the most at risk patients.

c) Subjects will continue to give meaningful, informed consent to participate throughout the study. They will see no significant decrease in their score on the informed consent quiz given every 6 months.

Analysis plan: A general linear model (GLM): ANOVA will be performed to compare the informed quizzes score results at 0, 6, and 12 months during the subjects' participation in the study.

5. Power Analysis: All calculations are based assuming a conventional medium effect size ($f=.25$, Cohen 1988); and a two-tailed alpha set at 0.05. Tuomilehto et al. estimated the SD of weight loss at roughly 5 kg across several treatment conditions (lifestyle changes vs. control) (76). A medium effect would thus translate into a group difference of about 2.5 kg or about 5.5 pounds. With an enrollment of $N=120$ and an estimated attrition rate of 45% we expect that at least 66 subjects will provide complete the study and provide 4 data points. The power analyses below are based on a sample size of $N=66$, i.e. this is a very conservative estimate due to the fact that the mixed linear model allows us to include cases with missing values in the analyses and that while they don't provide as much information as complete cases they still provide some information and will increase power. For the between-group comparisons, $N=66$ yields power=.7199 for main differences between groups if we assume that the within subject correlation is $r=.50$. Power to test for the difference in outcome trajectories of time – our main outcome variable is 0.99, and even if the effect is as small as $f=0.15$ we will have sufficient power to distinguish between the trajectories of the two treatment groups (power=0.83) insuring that we will get significant, insuring that we Preliminary data analyses shows that these assumptions are quite conservative and that effect sizes seem to be slightly larger than projected, suggesting that the final power will exceed the estimates presented here.

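### The primary Pearson tests for secondary hypothesis (a) define neither the weight-loss value nor how withdrawals enter, with 45% attrition expected; a model of all program-arm weights should be primary

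*Combined protocol and SAP*

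**What the plan says.** Under Statistical Plans, Secondary Hypotheses (a), the plan lists five associations with weight loss: negative symptoms, motivation to change, cognitive impairment, insight, and motivation on the URICA. The analysis paragraph states that "the primary tests of each of these hypotheses will be done by computing Pearson correlations between the specified variables within the treatment group". It then adds: "Supplementary analyses will be done within the context of the mixed effects designs described above". Those analyses test interactions with treatment group and are listed for items (i) to (iv).

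The paragraph does not say whether weight loss means change at month 12, change at the last visit or a fitted slope. It does not say when the predictor is measured, and it attaches no missing-data rule.

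Other sections bear on this:

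- **Power Analysis** assumes "an estimated attrition rate of 45" per cent.
- **Attrition** undertakes to "include all enrolled participants in analyses when any outcome data are available (intent to treat"). It also cites a methods comparison that "strongly cautions against analyses based only on complete cases" and speaks well of linear mixed models.
- **Repeated measures analyses** describes a slope for each participant with a baseline and at least one later measure.
- **Weight Loss Measures** and the Schedule of Events have weight taken at every visit.

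**The concern.** Elsewhere the plan's answer to missing data is a likelihood-based mixed model that uses whatever was observed. The primary test here is not such a model. With close to half the patients expected to leave, the result depends on what number stands for a withdrawn patient's weight loss, and the plan leaves that open. The possible definitions give different answers and could be chosen after the data are seen.

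If only patients with a month-12 weight count, the test loses nearly half its sample. If leaving is also related to the predictor, to early weight loss or to both, the remaining patients are selected on the variables being correlated. The trial could then report no link between, say, negative symptoms and weight loss when one exists.

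**Working it through.** **1. The plan's own figures.** Completers: 120 x (1 - 0.45) = 66. For the between-group test with f = 0.25, four measurements and within-subject correlation 0.50, the noncentrality is f²Nm / (1 + (m-1)ρ) = 0.0625 x 66 x 4 / 2.5 = 6.6. On 1 and 64 df this gives power 0.716 (stated 0.7199). For trajectories, 0.0625 x 66 x 4 / 0.5 = 33 on 3 and 192 df gives 0.999 (stated 0.99). At f = 0.15 the noncentrality is 11.88 and power 0.828 (stated 0.83). These figures reproduce, but they concern the group comparison. The plan gives no power for the correlations.

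**2. Patients available.** Allocation is not stated. Assuming 1:1 and equal attrition, 60 enter the program arm and 60 x 0.55 = 33 complete.

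**3. Effect of sample size alone.** Fisher's approximation, two-sided 0.05: power ≈ Φ(arctanh|r| x √(n-3) - 1.96). At r = 0.40, arctanh = 0.4236. For n = 33, 0.4236 x √30 = 2.320, less 1.96 is 0.360, so power is 0.64. For n = 60, 0.4236 x √57 = 3.198, less 1.96 is 1.238, so power is 0.89.

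| assumed true r (size) | n = 33 | n = 60 |
|---|---|---|
| 0.2 | 0.20 | 0.33 |
| 0.3 | 0.40 | 0.65 |
| 0.4 | 0.64 | 0.89 |
| 0.5 | 0.85 | 0.99 |

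The smallest correlation detectable with 80% power is tanh((1.960 + 0.842)/√30) = 0.47 at n = 33 and tanh(2.802/√57) = 0.35 at n = 60. The n = 60 column is an upper bound, because partly observed patients carry less information.

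**4. Simulation of dropout.** Inputs from the documents: the visit weeks, 45% attrition and an SD of weight loss of 5 kg. Assumptions: true r of -0.40, mean loss 3 kg, linear loss, 1 kg visit noise, and a dropout hazard proportional to exp(0.7 x predictor - 0.5 x (loss so far - 3 kg x time)/3), with terms switched off as needed.

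| dropout depends on | 12-month completers: mean r, power | all weights, random-slope model: standardised effect, power |
|---|---|---|
| nothing | -0.38, 0.60 | about -0.40, 0.82 to 0.84 in all three rows (about 0.84 under random dropout) |
| predictor | -0.34, 0.51 | |
| predictor and weight to date | -0.24, 0.29 | |

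Under random dropout the correlation is -0.38 rather than -0.40 because single weights carry visit noise. Step 3 at r = 0.38 and n = 33 gives Φ(0.400 x 5.477 - 1.96) = Φ(0.231) = 0.59, which agrees.

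**5. Definitions that keep withdrawals.**

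- *Last-available change* keeps power, but it mixes time in the program with rate of loss. With a true correlation of zero and predictor-related dropout, it rejects about 7% to 11% of the time at a nominal 5%.
- *Unweighted per-patient slopes* are noisy after short follow-up. A true -0.40 averages -0.22 to -0.25, with power 0.44 to 0.52.
- For comparison, *completers only* with a true zero and dropout on both factors averages +0.11 and rejects about 10%.

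**6. Sensitivity to dropout strength.** In a simpler calculation with true r of 0.30 in size, multiplying the odds of dropout by 2, 3 or 5 per SD of the predictor alone gives completer correlations of 0.29, 0.27 and 0.26. Multiplying the odds by 2 or 3 per SD of both the predictor and poor weight loss gives 0.20 and 0.12. Large bias therefore needs dropout linked to weight.

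**7. Sensitivity to the shape of loss.** If 70% of the loss occurs by week 8 (an assumption), a straight-line slope model is itself misled. With predictor-only dropout and a true zero it gives a spurious standardised effect of +0.16, while completer Pearson stays near zero. At a true -0.40 with dropout on both factors, its power falls to 0.73.

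**The case against.** The strongest reply is that the plan nowhere excludes withdrawals. One value per patient does not mean completers only. The general rule covers anyone with outcome data, weights exist at every visit, and the plan describes a slope for anyone with two measures. That stands: a reader might infer that the plan has chosen a complete-case analysis, and the text does not say so. The defect is that the value and the rule are missing. Step 5 shows that the definitions which keep withdrawals do not remove the problem.

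A reader might also infer that high-symptom, low-motivation patients are the ones who leave. The documents give no dropout rates by these characteristics. Under Minimizing Risks, patients judged worse on the CGI are discharged, so some exits are symptom-linked. That rule concerns overall worsening, not baseline negative symptoms, cognition, insight or motivation. The plan also expects data to be missing at random. Dropout driven by baseline predictors and recorded weights fits that assumption, but the assumption protects a likelihood-based model, not a completer correlation.

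The supplementary moderator models do keep partly observed patients. They ask a different question, whether the treatment effect varies with the predictor across both arms, and usual-care patients may enter the program after six months.

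Two further inferences fail. URICA motivation is not left out of those models: they include motivation to change, which the hypotheses say the URICA measures, so items (ii) and (v) overlap and only the numbering is loose. Nor does the aim of identifying who benefits rest on these correlations, since the plan also assigns it to recursive partitioning.

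**Conclusion.** The concern holds as a gap in specification with a better method at hand. The primary tests for secondary hypothesis (a) need a weight-loss value and a rule for withdrawals, and have neither.

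The firmest cost is power: on a 12-month reading, about 0.60 against about 0.84 at an assumed correlation of -0.40, even if dropout is random. Attenuation is modest (about -0.34) if dropout depends on the predictor and strong (about -0.24) only if it also depends on weight to date.

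These figures rest on 1:1 allocation, equal attrition, an assumed true correlation, linear loss and assumed dropout strengths, none of which the documents supply. The all-weights model is better under those assumptions but not unconditionally: a strictly linear slope is unreliable if most loss falls in the intensive phase. The hypothesis is secondary, so the primary comparison of the arms is unaffected.

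**What to change.** - For each predictor, make the primary test the effect of baseline predictor by time in a mixed model of all program-arm weights, from baseline to withdrawal or month 12. State that every scheduled weight enters, since the plan elsewhere lists only four assessment times for its repeated-measures analyses.
- Model time by visit, or with separate intensive and maintenance phases, unless linearity is supported. Test the predictor's association with the modelled 12-month change. Fix the random-effects structure in advance.
- State that predictors are baseline values.
- Report Pearson correlations as descriptive, with the weight-loss value defined and the number of patients shown.
- Align motivation items (ii) and (v) across the hypotheses and the moderator list.

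The cost is SAP wording. The mixed model is already planned and weight is already recorded at every visit. The drawbacks are that the result is a model coefficient rather than a familiar r, although it can be standardised, and that it depends on the time shape chosen.
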